The IntelliCare intervention consists of 2 components: (1) a patient-facing app for assessment and self-management of depression, (2) a Care Manager dashboard. A brief description of each component appears below:

1. Patient-facing app: The patient-facing app contains the following tools for the assessment and self-management of depression:
 - Assessment: Within the IntelliCare App, participants will be prompted to complete an assessment of current (within the prior 2 weeks) depressive and anxiety symptoms.
 - Self-management: IntelliCare depression and anxiety self-management modules will be used in the trial. Each module represents a single behavioral strategy (e.g., scheduling positive behaviors, thought restructuring, goal setting), and takes only a few seconds to use. The modules address specific treatment goals, and may include instructional content as well as interactional components (e.g., activity scheduling/monitoring, thought records) that support behavior change. All participants will download the main app onto their own phones and will be encouraged to use the modules as directed by the CM throughout the study period.
2. Care Manager Dashboard: The CM dashboard displays which modules are being used by which patients, supporting efficient triage and clinical decision making. The dashboard also includes mental health assessment scores, a place to document notes about patient interactions, and a text messaging interface.

Enhanced Treatment as Usual (eTAU)

The eTAU will consist of current care plus access to a website (compass-care.northwestern.edu) that will provide content specific to perinatal depression. Patients randomized to eTAU will communicate with their Care Managers using phone or MyChart, which is consistent with standard clinical practice.

PROCEDURES INVOLVED

This is a multi-pronged prospective investigation of a TES to improve collaborative care service delivery to people with perinatal depression. Participants will be enrolled in a pragmatic RCT with outcome assessments at baseline, 6 and 12 weeks.

Data will be gathered from study participants as outlined in the table below. We have described how data collection methods differ by randomization assignment where applicable.

STU#:00211815

Table 1. Effectiveness Measures

Outcome/Construct	Measure Name	Method	Timing

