Emotional Discomfort: Participants will be informed that their participation in the study is entirely voluntary and that they may stop at any time without affecting their access to medical care. Participants will be told that they may decline to answer any questions or complete any procedures.

Plans for Ensuring Safety and Suicide Prevention: The development of suicidal ideation during the study remains the most serious risk. Patient safety always takes precedence over study protocol. All suicidality procedures are managed directly by the patient's care management team or through research staff including [name], [name], and [name]. The CMs are licensed clinical social workers who have completed Mental Health First Aid trainings and have been trained in suicide risk management as part of their regular job duties. CMs are buttressed by the COMPASS psychiatrists, the obstetricians, and the Asher Center (see Letter of Support from [name]) who are available for clinical support. Research staff are trained in suicide risk management as part of their regular job duties. Research staff are buttressed by clinical psychologists and are available for clinical support.

There are a number of pathways through which suicidal risk can be detected. During the trial phases, suicidality is detected through automated PHQ-9 self-report assessments, direct communications with the Care Managers via phone or messaging (email, text, etc.), or direct communication with research staff during user feedback interviews. In each of these instances, the goal is to rapidly acquire additional information that can trigger safety procedures if necessary. When suicidality is expressed by the participant directly to the research staff in a usability interview or other direct communication, the research staff follows up to conduct a risk assessment based on the Columbia Suicide Severity Rating Scale and engage the participant in risk management procedures based on their risk status.

All participants in the trial or pre-enrollment receive automated self-report assessments. If a participant rates Question 9 of the Patient Health Questionnaire-9 (i.e., "Over the last 2 weeks, how often have you

STU#:00211815

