been bothered by thoughts that you would be better off dead or of hurting yourself in some way") a 1 or higher, a second suicidality question from the Beck Depression Inventory (BDI) is administered that is more specific in identifying suicide risk. Participants who indicate that they would like to kill themselves, or would kill themselves are considered "at risk." All CMs are notified via an alert in the TES and/or by the research team directly via email within one business day. The first CM to receive the notification will call the patient for a risk assessment based on the Columbia-Suicide Severity Rating Scale by phone within one business day. If an acknowledgement is not made by a CM, a member from the research team or clinical supervisor will follow up with the CM. Once acknowledgement is made by the CM, the Columbia-Suicide Severity Rating Scale is conducted as a routine part of clinical care. For patients who are at greater than low risk, the CM takes all necessary actions to ensure the safety of the patient, including considering the use of psychiatric hospitalization. If the patient does not respond to contact attempts from the CM, the patient's medical emergency contact, on file for all COMPASS patients, is called to assist in contacting the patient. In the rare event that contact cannot be made, CM's may contact emergency services for a wellness check in accordance with COMPASS procedures. When suicidality is expressed by the patient directly to the CM, the CM similarly follows up to conduct an evaluation and perform safety procedures. Perinatal psychiatrists are available for consultation with CMs and for follow-up consultation with any patient perceived to be at risk. For patients who are not at immediate risk and who do not require hospitalization, an outpatient psychiatric evaluation may be coordinated by the CM. A member from the research team or the clinical supervisor will follow up if the CM does not within two business days.

We note that these are risks inherent in the population and would occur whether or not they were enrolled in the study. We do not believe that the risk of these depressive, suicidal, or other adverse outcomes are increased as a function of being enrolled in this study or receiving TES during the trial phases. All potential risks associated with participation in this study are disclosed in consent documents.

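### On the automated suicide-risk pathway, a positive PHQ-9 Question 9 followed by a blank BDI item triggers no stated alert or timed follow-up

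*Protocol*

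**What the plan says.** The rule is in the Protocol, Protection Against Risks, under Plans for Ensuring Safety and Suicide Prevention. The SAP does not touch it.

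- **Who is screened:** "All participants in the trial or pre-enrollment receive automated self-report assessments".
- **First step:** "If a participant rates Question 9 of the Patient Health Questionnaire-9" at 1 or above, a more specific BDI suicidality item is shown.
- **Classification:** "Participants who indicate that they would like to kill themselves, or would kill themselves are considered" to be at risk.
- **Alert:** the next sentence reads "All CMs are notified via an alert in the TES and/or by the research team directly via email within one business day". It states no condition of its own.
- **Response:** the first CM to get the notification phones the patient for an assessment based on the Columbia-Suicide Severity Rating Scale, also within one business day.
- **Backups:** research staff or a clinical supervisor step in if no CM acknowledges the alert, or if the CM has not followed up within two business days. A further rule, beginning "If the patient does not respond to contact attempts from the CM", leads to the emergency contact and possibly a wellness check.

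The Emotional Discomfort paragraph just before this plan says: "Participants will be told that they may decline to answer any questions or complete any procedures".

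**The concern.** The pathway has two stages, and the second can be left empty. Someone who has just reported thoughts of death or self-harm may skip the BDI item or close the survey there. That person has not indicated a wish or intent to die, so does not meet the at-risk definition, and the alert appears to hang on that definition. A blank then ends the same way as a reassuring answer, although it reassures nobody.

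What is at stake is participant safety. The Protocol itself ranks emerging suicidal ideation as the gravest risk in the study. An automated rule does only what it is told, and here it is told nothing about a missing answer.

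**Working it through.** No figure in the plan needs reproducing. The check is to trace each branch of the automated pathway and then look for any other rule that catches the open one.

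| Question 9 | BDI item | Stated result |
|---|---|---|
| 0 | not shown | none needed |
| 1 or more | would like to, or would, kill self | at risk; alert, responder and deadlines all stated |
| 1 or more | answered below that level | not at risk; no alert stated |
| 1 or more | blank | no alert or deadline stated |

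The third row is a triage decision made with information. The fourth has none to go on.

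**Do the backups reach the fourth row?** No. Two concern a CM who does not acknowledge or act, and one concerns a patient who cannot be reached after a CM has tried. All three presuppose that a notification went out.

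**Do the other detection routes reach it?** They need suicidality to be voiced directly to a CM or to research staff. A blank survey item is neither.

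**Does general text reach it?**
- The plan says: "In each of these instances, the goal is to rapidly acquire additional information that can trigger safety procedures if necessary". This is an aim, with no actor or time limit for this case.
- The same section puts safety above protocol and assigns suicidality procedures to the care team or research staff. That is a general owner without a trigger.
- Under IntelliCare, Care Manager Dashboard: "The dashboard also includes mental health assessment scores". No review interval and no Question 9 flag is given.
- Table 1 takes eTAU PHQ-9 data from routine care and lists the Columbia assessment as needed. Neither is tied to a missing BDI answer.
- Under Data Management, Care Manager and Research Team Data Entry, CMs cannot open participants' self-report surveys in REDCap. Table 1 shows that TES PHQ-9 data come partly through REDCap. There, detection rests on the research team, which has no instruction for a blank.

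**Workload of a fix.** Inputs from the Protocol: 85 participants (Study Summary, Study Endpoints) and assessments at baseline, 6 and 12 weeks. Assumed, because the documents give no rates: 10–30% of screens positive on Question 9, and 2–10% of those with a blank BDI item.

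- Scheduled screens: 85 × 3 = 255.
- Low: 0.10 × 0.02 = 0.002; 255 × 0.002 = 0.51.
- High: 0.30 × 0.10 = 0.03; 255 × 0.03 = 7.65.

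That is about 0.5 to 8 extra calls. In-app screens would add to this, but their frequency is not stated; the two weeks mentioned for the app is a symptom recall window, not a schedule. These numbers count calls, not missed at-risk patients.

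**The case against.** The strongest reply has four parts.

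1. **The forms are unseen.** The Protocol says the surveys and data-entry forms were uploaded for IRB review. If the BDI item cannot be left blank, the gap closes apart from an abandoned survey. This stands as a condition on the finding, although a forced answer would sit awkwardly with the right to decline.

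2. **The notification sentence is unconditioned.** It could cover every positive Question 9. That is possible, but the BDI item and the at-risk label would then have no stated role in the alert. If it is the intended meaning, one clarifying sentence settles the matter.

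3. **People are watching.** A reader might infer that nobody is responsible for these patients, or that CMs are blind to a positive PHQ-9. The documents do not support either. Suicidality procedures have a general owner, CMs monitor depressive symptoms as part of routine care, TES scores appear on the dashboard, and eTAU scores come from clinical care. Each documented PHQ-9 also prompts a record of whether stepped care was carried out, though that is keyed to the total score. The section on monitoring participant safety adds that significant symptoms reported to the study team lead to referral, but without a deadline or a statement that a survey response counts. All this narrows the exposure without supplying a rule for the blank item.

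4. **A protocol need not list every missing-item branch.** True in general. This branch follows a positive suicidality screen, so it deserves more than silence.

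**Conclusion.** The point holds in a limited form. As naturally read, the automated pathway gives no alert and no timed follow-up when Question 9 is 1 or more and the BDI item is blank. This rests on two things the documents leave open: that the forms allow a blank, and that notification is not already sent for every positive Question 9. The exposure is clearest for a PHQ-9 self-reported in REDCap.

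The size of any harm cannot be derived, because neither endorsement nor skip rates are given. It would be wrong to read the 0.5 to 8 calls as missed suicidal patients; that range is the burden of the remedy under assumed rates. Nor do the documents show that any such case would go unnoticed in practice. What they show is that noticing it is left to general vigilance and not to a rule.

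**What to change.** Add to Plans for Ensuring Safety and Suicide Prevention:

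- If Question 9 is 1 or more and the BDI item has no answer, whether skipped or because the survey was closed, the CMs are notified within one business day. For REDCap this is by research team email; for IntelliCare, by app alert or the same email.
- A CM then attempts contact for a Columbia-Suicide Severity Rating Scale assessment within one business day.
- The emergency-contact call and wellness check do not follow automatically from a blank answer; they are left to CM clinical judgement.
- Participants are told at consent that a blank here may prompt a call, so the right to decline stays intact.

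If every positive Question 9 is already notified, say so instead.

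**Cost.** One or two protocol sentences, a consent sentence, and a small form or vendor change. The vendor's price is not given, but the email route already exists and can serve IntelliCare too. The extra calls are few under the assumed rates, and some will go to people who merely declined a question. Giving blanks the full at-risk steps would bring in emergency contacts and possible wellness checks for those people, with a cost in confidentiality and pressure to answer. Leaving these steps to judgement avoids that, at the price that some who do not respond may be reached later.

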certain data entry forms in the database, and will not be able to access data from participant self-report surveys or interviews.

Interview Data

Audio recordings of interviews will be stored on the secure FSM ResFiles server. Interview audio files may be transcribed by the following NU transcription vendor: GMR Transcription, <https://www.gmrtranscription.com/>

Audio files will be shared with GMR Transcription through the vendor's proprietary web-based application for secure file management. The resulting transcripts will be stored on the secure FSM ResFiles server and accessed by study team members for coding purposes.

Numbers will be used to identify any written study materials, such as interview notes, and no personal identifiers will be on such materials.

TES Intervention Data Gathered by Adaptive Health

All IntelliCare intervention data will be gathered and securely managed by Adaptive Health during the trial. Per the terms of the Master Service Agreement that is in place between NU and Adaptive Health, at the end of the trial, Adaptive Health will transfer study data to the NU team and delete all identifying information. Table 5 below includes a description of the data elements that will be handled by Adaptive Health.

Table 5. Data Elements Handled by Adaptive Health

IntelliCare System Component	Data Elements Handled by Vendor
IntelliCare App	Identifiers (e.g. email address) to generate user login and create a unique ID that will then follow each user, app use event data (e.g., number of logins, time spent reviewing written information in the app), survey responses (PHQ-9, GAD-7, and suicidality assessment questions), and patient-entered information (e.g. journal entries).
IntelliCare Care Manager Dashboard	Dashboard usage use event data (e.g., number of CM logins, time spent reviewing records in the dashboard), CM notes about study participants (including a field to document participant names for accurate identification of patients in the dashboard).
Text Message Communication	Phone number used to facilitate sending/receiving text messages between study coach and participant, log of messages exchanged between study coach and participant

Links to Adaptive Health's privacy policy and terms and conditions are provided below:

<https://www.adaptive-health.com/privacy>

<https://www.adaptive-health.com/terms>

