- Severe: An experience that requires therapeutic intervention. The experience interrupts usual daily activities. If hospitalization (or prolongation of hospitalization) is required for treatment it becomes an SAE.

The study uses the following AE attribution scale:

- Not related: The AE is clearly not related to the study procedures (i.e., another cause of the event is most plausible and/or a clinically plausible temporal sequence is inconsistent with the onset of the event).
- Possibly related: An event that follows a reasonable temporal sequence from the initiation of study procedures, but that could readily have been produced by a number of other factors.
- Related: The AE is clearly related to the study procedures.

SAEs and specific treatment-associated AEs are reported to the IRB and NIMH program officer within 24 hours.

Data Safety Monitoring Board (DSMB)

The DSMB will be chaired by [name], from Kaiser Permanente, Seattle. [name] is a well-respected mental health researcher. As chair of the DSMB, [name] will appoint additional board members as needed and will determine the meeting schedule. That said, we expect that the DSMB will meet twice in the first year of the trial and once in the final year. The PIs, [name], and [name] (biostatistician) will be present to facilitate the flow of information, however they will not be voting members.

PROVISIONS TO PROTECT THE PRIVACY INTERESTS OF PARTICIPANTS

Potential participants will be identified by the CM. Prior to being consented, candidates will receive information about the study. Candidates who decline the consent procedure or who are screened out will have any identifying information removed from study records. Consent for the study will then be managed by research study personnel, rather than the CM. The study team will not release the identity of any participant to any non-authorized individual, except as is necessary for participant safety or regulatory review.

STU#:00211815

ECONOMIC BURDEN TO PARTICIPANTS

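### Suicide-risk alerts: read in sequence, the notify and call limits allow up to 4 calendar days, and answers given in REDCap have no evident automatic route to care managers

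*Protocol*

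**What the plan says.** All of this is in the Protocol; the SAP does not touch it.

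Under Plans for Ensuring Safety and Suicide Prevention, everyone in the trial, and people not yet enrolled, receive automated self-report assessments. A score of 1 or more on PHQ-9 item 9 brings up a BDI item. A participant who answers that they would like to kill themselves, or would do so, is classed as at risk. Then:

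- Notification: "All CMs are notified via an alert in the TES and/or by the research team directly via email within one business day".
- Call: "The first CM to receive the notification will call the patient for a risk assessment", and this is to happen "by phone within one business day".
- No acknowledgement: "If an acknowledgement is not made by a CM, a member from the research team or clinical supervisor will follow up with the CM". No time limit is attached.
- Later in the same paragraph, after a sentence on outpatient psychiatric evaluation: "A member from the research team or the clinical supervisor will follow up if the CM does not within two business days". No starting event is given.

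The same section sets the aim for every detection pathway, including the automated PHQ-9: "the goal is to rapidly acquire additional information that can trigger safety procedures if necessary".

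Under Care Manager and Research Team Data Entry, care managers see only certain forms in the REDCap database and "will not be able to access data from participant self-report surveys or interviews". Table 1 says that TES depression and suicidality data come through IntelliCare and REDCap, while eTAU data come from routine COMPASS care.

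**The concern.** The participants at this step have just disclosed a wish or intent to kill themselves, and the Protocol calls suicidal ideation the most serious risk in the study. Two features of the written pathway allow delay that could easily be avoided.

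First, there are two limits of one business day each, and the second attaches to the care manager who has received the notification. The permitted time from answer to call is then the sum of the two, and a weekend stretches it. Because the start of the second limit is not stated, staff cannot tell from the text when a call is late.

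Second, some automated answers are recorded where care managers cannot see them. For those answers the first interval depends on a member of the research team noticing the answer and sending an email.

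**Working it through.** The Protocol states no end-to-end time, so there is no figure to reproduce. The check is a count of business days.

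**Inputs from the Protocol.** Notification limit: 1 business day. Call limit: 1 business day. Start of the call limit: not stated.

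**Assumptions.** A business day is Monday to Friday. Within n business days means by the end of the nth Monday-to-Friday day after the day of the answer. An answer may arrive on any day of the week. There is no public holiday. The Protocol defines none of these.

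**Formula.** Permitted calendar days = (date of the nth business day after the answer) − (date of the answer), where

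- limits in sequence: n = 1 + 1 = 2
- both limits running from the answer: n = 1
- immediate notification, then the call limit: n = 0 + 1 = 1

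| Day of answer | n = 2 | n = 1 | Difference |
|---|---|---|---|
| Monday | 2 | 1 | 1 |
| Tuesday | 2 | 1 | 1 |
| Wednesday | 2 | 1 | 1 |
| Thursday | 4 | 1 | 3 |
| Friday | 4 | 3 | 1 |
| Saturday | 3 | 2 | 1 |
| Sunday | 2 | 1 | 1 |
| Maximum | 4 | 3 | |
| Mean, answers spread evenly | 19/7 = 2.7 | 10/7 = 1.4 | 9/7 = 1.3 |

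Example: after a Thursday answer, notification is due by Friday and the call by Monday, which is 4 days. If notification is immediate, the call is due by Friday, which is 1 day. The means are averages of permitted maxima, not expected response times.

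**Sensitivity.** A Monday holiday raises the sequential maximum from 4 to 5. If an after-hours answer counts as received on the next business day, the sequential maximum is 5, or 6 with the holiday. With immediate notification under that same after-hours rule, the count is 1 (receipt) + 1 (call) = 2 business days. That is the n = 2 column, with a maximum of 4.

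**Routes, by arm and data source.**

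| Source of the answer | Route to the care manager evident in the Protocol |
|---|---|
| TES, entered in the app | TES alert; the dashboard also shows assessment scores |
| TES, entered in REDCap | Research-team email only, since care managers cannot open survey data |
| Any automated survey sent to eTAU or pre-enrollment participants | Research-team email only, since IntelliCare and its dashboard are TES components |
| eTAU, score collected in routine COMPASS care | The care manager may learn of it directly, with no notification step |

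The Protocol joins the two notification routes with and/or, and does not say which one covers which row.

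**The case against.** The limits are maxima, and staff may act much faster. The aim of acting rapidly has no number, so nothing here is a numerical contradiction. The sequential reading is an interpretation: if both limits run from the answer, the maximum is 3 days, not 4. Other detection pathways exist, including direct contact with care managers or research staff. All of this stands, and it makes the point one of ambiguity and avoidable delay rather than error.

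The documents do not support four stronger readings that a reader might infer:

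- **Contact comes later in eTAU by design.** One outer limit covers both notification routes, and the TES alert is never called immediate. If it is immediate, the worst case is 4 days by email against 3 by alert. But TES answers in REDCap go by the email route too, and an eTAU care manager who collects the score needs no notification.
- **The two-business-day sentence is the safety net for a missed first call.** It follows directly on the coordination of outpatient evaluation for patients not at immediate risk, and may refer to that. A missing acknowledgement has its own step earlier in the paragraph.
- **Nobody is responsible because every care manager is told.** The acknowledgement and escalation step addresses this, and telling all care managers is a defensible way to cover absences.
- **The 24-hour reporting limit for serious adverse events shows a misplaced priority.** That limit governs reports to oversight bodies, and a positive BDI item is not in itself a serious adverse event under the Protocol's definition.

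**Conclusion.** The point holds as a low-cost improvement. As written, the pathway permits up to 4 calendar days from an at-risk answer to a call over an ordinary weekend if the limits run in sequence, and 3 if both run from the answer. Neither figure is a firm ceiling, because holidays and after-hours receipt can lengthen both. The result rests on a Monday-to-Friday business day and on answers being possible on any day.

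For answers given in REDCap, a research-team email is the only evident route to the care manager. On the sequential reading, removing the separate notification interval takes up to one business day off the permitted time: 1 calendar day on most days of the week, and 3 for a Thursday answer. On the other reading the maximum stays at 3, and the gain is that a manual notification no longer uses up the time allowed for the call. A systematic difference between arms is possible but not established.

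**What to change.** 1. Set the REDCap survey to send an automatic notification to the care managers and the research team when an at-risk answer is submitted, whatever the arm and including pre-enrollment surveys. The separate notification interval then drops out.
2. State in the Protocol which notification route covers each arm and each data source.
3. Reconcile Plans for Ensuring Safety and Suicide Prevention with Care Manager and Research Team Data Entry. Say when the call and acknowledgement limits start, what the two-business-day follow-up refers to and when it starts, what a business day means outside working hours, and how these limits serve the stated aim of acting rapidly.

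The response time and the responsible clinician are for the clinical team to set; none is proposed here.

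Cost: a small survey set-up task, a reworded paragraph, and a stated rule for handling notifications that arrive outside office hours. That rule affects the gain, as the after-hours count shows.
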